**C.1.c. Functional Magnetic Resonance Imaging (fMRI)**

**Exerience.** [name] (Co-I) developed a Cannabis Cue Reactivity (CCR) fMRI task consisting of cannabis and neutral images that is useful for probing the neurobehavioral effects of gabapentin: 1) cue reactivity appears to be GABA/GLU mediated, 2) cue reactivity/craving are important clinical targets, and 3) reward sensitivity (congruent with the RDoC construct, Approach Motivation), arguably best characterized by CCR in CUD+BD, is a core neurobehavioral deficit in both CUD and BD.

**Figure 3. Robust activation was elicited from cannabis, vs. neutral, stimuli in heavy cannabis users in reward regions including the medial prefrontal cortex, anterior cingulate and striatum.**

Preliminary data, from 41 heavy (M=2x/day) cannabis users (46% women, M age=18.7 ±0.51) demonstrated significant activation to cannabis vs. neutral cues (cluster-corrected z > 2.3, p < 0.05) in regions involved in reward processing, including bilateral medial prefrontal, striatum, dACC, subcallosal, precuneus, and posterior cingulate cortex (Figure 3). As noted in C.2.e (Procedures), the proposed response inhibition ("go no-go") fMRI task, included to better target dACC activation) has been featured in a number of PI-authored publications.

**C.2. Research Design and Methods.** The proposed 2-week, double-blind crossover study will evaluate: a) the effects of gabapentin on basal dACC and rBG GABA and GLU concentrations and b) the effects of changes in GABA and GLU levels on brain activity to cannabis and response inhibition (impulsivity) cues. The relationship between changes in GABA and GLU levels, brain activation to cannabis/response inhibition cues, and clinical symptoms (e.g., cannabis use, impulsivity, mood and anxiety) will be explored. Participants will complete two, 1-week experimental conditions (gabapentin, placebo) in a randomized order. Each condition will consist of a visit for assessment and dispensing of medication (Day 1), titration to maximum dose (1200mg/day) (Days 1-5), MRI (Day 5), and medication washout (Days 5-7). Spacing of appointments cited throughout the protocol refers to ideal conditions which may be minimally deviated from if needed (e.g., +/- 1 day between medication and MRI visits, 1 week between conditions). See Figure 4 below for a full study design schematic.

[figure not shown]

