the study if the provider feels it is appropriate. Concerning the RHJVAMC, we will seek separate approval through the VAMC to post and distribute VA-approved study fliers.

Table 1. Schedule of events by study visit					
Study Visit	Visit 1 Evaluation	Visit 2 Med Disp	Visit 3 MRI	Visit 4 Med Disp	Visit 5 MRI
Clinician and PA					
Informed Consent* / HIPAA* / BrAC contract*	X				
SCID-5 (Mood/Substance)*	X				
TLFB* (90 day at V1)	X	X	X	X	X
YMRS* / MADRS* / C-SSRS*	X	X	X	X	X
BDRS / BR		X	X		X
Observe Dose (note time)		X	X	X	X
H&P* / Metal Screen*	X				
AEs / Vitals		X	X	X	X
Self-Report					
Demographics / Family history	X				
BDI* / PSQI* / BAI*	X				
BIS-11 / SPSRQ / AUDIT / ASRS / WHODAS / DSM-5 PID5/PQ	X				
BDI PW / PSQI PW / BAI PW (PW=Past Week)		X	X		X
FTND / ASRM / MCQ / CWS	X	X	X		X
Actiwatch Data Download			X	X	X
Urge to use MJ [1-10] (PRE/POST MRI)					X
Computer Tasks					
STOP-IT	X		X		X
Delay Disc	X				
GoGoNoGo Practice			X		
CNL Labs					
CMP* / CBC* / DNA*	X				
%dCDT		X			
Gabapentin level			X		X
EtG		X	X		X
Riboflavin		X	X		X
Cannabinoids/Creatinine Levels		X	X	X	X
In-House Labs					
Collect urine specimen* / UDS*	X	X	X	X	X
Breathalyzer*	X	X	X	X	X
Pregnancy Test*	X		X		X
Saliva drug screen		X	X		X

Note: "\*" Indicates assessments that must be done at Visit 1. Non-starred assessments at Visit 1 can be completed at Visit 2 if needed.

**C.2.e. Procedures.** See Table 1.

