**MRI (Visits 3, 5).** MRI visits will take place on day 5 of each condition. Participants will be asked to abstain from drugs/alcohol  $\geq 12$  hours prior to MRI. They will take their final dose of medication in front of study staff, 1 h prior to MRI, to ensure compliance. Participants who smoke will be allowed to have their last cigarette immediately prior to their final medication dose. Mood symptoms (YMRS, MADRS, C-SSRS, BDI, BAI, ASRM, PSQI), alcohol/drug/tobacco consumption (TLFB, UDS, FTND, EtG, Saliva), cannabis withdrawal (CWS), and cravings (MCQ) will be assessed. Participants will provide a urine and blood sample to test for gabapentin levels, riboflavin, liver function, and alcohol/drug consumption. Following structural and H-MRS scanning, participants will complete the CCR and go no-go fMRI tasks in counterbalanced order (see below) with the Natural Rewards Task at the end. fMRI tasks will be conducted while acquiring BOLD weighted transverse scans using a gradient-echo, echo-planar imaging (EPI) sequence: TR/TE=2200/35 ms; flip angle=90°; field of view=220x220 mm; voxel size=3.00x3.00 mm; 37 contiguous 3-mm-thick slices. Total scan time is approximately 75 m in a Siemens 3.0T Prisma (32-channel head coil). Participants will discontinue study medication following each MRI and will remain off study medication on days 6-7 of the condition. Given that the last gabapentin dose will be taken in the morning of day 5, this will provide approximately 11 half-lives of elimination prior to the start of the next condition. Crossover studies employing up to 3x the proposed dose of gabapentin have demonstrated an absence of carryover effects on clinical outcomes given the same or fewer days of washout as proposed herein. Potential carryover effects will be carefully examined using the proposed analytic design. Outside of the scanner, participants will complete the STOP-IT task. Within approximately 72 hours of day 7 of the final study condition, participants will be contacted by clinically-trained study staff to discuss adverse events, alcohol and drug consumption, and mood stability since discontinuing study medication.

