**Data Analysis.** Generalized linear mixed effects models will be employed to assess the effect of gabapentin on dACC and rBG GABA levels (Hypothesis 1). As detailed above, whole-brain random-effects analyses will be conducted to assess the direct effect of gabapentin, as well as the direct effect of gabapentin-induced changes in GABA, on brain activation to cannabis and response inhibition (impulsivity) cues (Hypothesis 2). These analyses will be supplemented with a region of interest approach (extracting % signal change from participants’ H-MRS voxels) using the MarsBaR SPM toolbox. Primary models for Hypotheses 1 and 2 will contain the main effect of treatment, period (scan 1 v. scan 2), and sequence (gabapentin 1st v. placebo 1st) to ensure the crossover design and washout were successful. All models will be re-estimated with GLU levels entered in place of GABA (Exploratory Hypothesis 1). To synthesize hypotheses 1-2, mediation models will be estimated in which metabolite levels are posited as mediators of the association between medication treatment and brain activity to

cannabis and response inhibition cues. We will employ previously successful methods to minimize attrition, but mixed effects models can be used to provide valid estimates assuming data are missing at random^112.

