#### **d. Potential Risks**

1. Medication side effects. Gabapentin is generally well-tolerated, with sedation and dizziness being the most commonly reported side effects. Although the FDA has issued a class warning for antiepileptic drugs and suicidal thoughts and behavior, available data do not support an association between gabapentin, specifically, and increased suicidal ideation or behavior in individuals with BD or other psychiatric populations. The proposed study will minimize potential medication-related risks by implementing low starting doses and titration of study medications and will carefully monitor potential medication-related risks via biweekly scheduled visits and assessment of adverse events (including assessment of suicidal ideation and behavior at each and every study visit). The study physician will determine if the participant should be discontinued from the medication due to adverse drug reactions and will treat clinically as needed. Any confirmed incidence of serious adverse events that are deemed probably or definitely due to the study medication will result in immediate discontinuation of the study medication and follow-up assessments will be conducted until resolution. Subjects will be referred for treatment as necessary.
2. Drug interactions. Azelastine, orphenadrine, oxememazine, paraldehyde, and thalidomide are contraindicated in patients taking gabapentin; as such, individuals taking these medications will be excluded. As noted earlier, participants will be required to be taking a stable pre-existing regimen of at least one FDA-approved mood stabilizing medication treatment for BD. There are no known serious drug interactions with gabapentin and mood-stabilizing medications.

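### Go/no-go practice is scheduled only at Visit 3, on study capsules, so condition order decides whether participants are trained on gabapentin or placebo; training everyone before the first dose removes this asymmetry cheaply

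*Combined protocol and SAP*

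**What the plan says.** In Table 1 (Schedule of events by study visit), under Computer Tasks, the row "GoGoNoGo Practice" has a single mark, at Visit 3. Visits 1, 2, 4 and 5 are blank. The only computer tasks before dosing are STOP-IT and delay discounting at Visit 1.

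C.2 states: "Participants will complete two, 1-week experimental conditions (gabapentin, placebo) in a randomized order". No allocation ratio is given. Under MRI (Visits 3, 5) in C.2.e, "MRI visits will take place on day 5 of each condition" and "They will take their final dose of medication in front of study staff, 1 h prior to MRI, to ensure compliance". At both visits "participants will complete the CCR and go no-go fMRI tasks in counterbalanced order".

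The same section defends the washout by counting about 11 half-lives and citing crossover studies that "have demonstrated an absence of carryover effects on clinical outcomes". It promises to examine carryover through the analysis. Data Analysis in C.2.f says "Primary models for Hypotheses 1 and 2 will contain the main effect of treatment, period" and sequence, and plans to test the direct effect of gabapentin on activation as part of the Hypothesis 2 work. C.2.a lists order effects among the things to be examined.

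**The concern.** At Visit 3 everyone has been on study capsules since day 1. Whether the practice falls before or after that day's observed dose, the state in which a participant is trained is fixed by condition order. Under 1:1 order, half would be trained on gabapentin.

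Potential Risks describes gabapentin as having "sedation and dizziness being the most commonly reported side effects", and the protocol proposes that the drug acts partly through impulsivity, which this task probes. A difference between training on drug and training on placebo is therefore conceivable.

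Such a difference would behave as unequal carryover. The washout argument is about drug elimination and clinical outcomes, whereas what has been learned stays learned. At stake is the direct gabapentin effect on the no-go versus go contrast.

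**Working it through.** **The plan's own figure.** The plan enrols 23 to obtain 18 completers at 20% dropout: 18 / 0.80 = 22.5, rounded up to 23. This reproduces. With 1:1 order (an assumption), 18 completers give 9 per order.

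**Model.** Take one activation summary per scan, such as percent signal change from a spectroscopy voxel, in units of its between-person SD. Let τ be the drug effect, π the learning common to both orders, and λ the extra shift at scan 2 when training was on gabapentin.

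| Order | Scan 1 | Scan 2 |
|---|---|---|
| Gabapentin first | μ + τ | μ + π + λ |
| Placebo first | μ | μ + π + τ |

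Mean of scan 1 minus scan 2: τ − π − λ for gabapentin first, and −π − τ for placebo first. Half the difference between orders is the treatment estimate:

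(2τ − λ)/2 = τ − λ/2.

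So π cancels and the bias is −λ/2. Difference between orders in the sum of the two scans: (2μ + τ + π + λ) − (2μ + π + τ) = λ. The sequence term thus estimates λ itself, but from between-person totals.

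**Limit of the model.** It places λ at scan 2 only. If training on drug also moved scan 1 by δ, the estimate would be τ + (δ − λ)/2. A shift of equal size at both scans would cancel, so λ is to be read as the net scan-2 shift.

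**Common learning only (λ = 0).** In simulation with π = 0.5 or 1.0, the bias is 0.00 and the type I error 5%, for 9/9 and for 7/11 splits. Without a period term, a 7/11 split would give bias of (11 − 7)/18 × π = 0.11 or 0.22. The period term does its job.

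**Order-specific learning (τ = 0, 9 per order, two-sided 5%, 16 df).** The between-scan correlation is taken as r = 0.60. This is the planning value for GABA; none is given for activation.

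- Treatment test: SD of a within-person difference = √(2(1 − 0.60)) = 0.894. Noncentrality = λ / (0.894 × √(2/9)) = λ / 0.422.
- Sequence test: SD of a total = √(2(1 + 0.60)) = 1.789. Noncentrality = λ / (1.789 × √(2/9)) = λ / 0.843.

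| λ (SD) | Bias in τ (SD) | Treatment test rejects a true null | Power of sequence test |
|---|---|---|---|
| 0.25 | −0.125 | about 9% | about 6% |
| 0.5 | −0.25 | about 20% | about 9% |
| 1.0 | −0.50 | about 60% | about 20% |

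If the shift is instead measured in SDs of the within-person difference, no correlation is needed. The noncentrality is then d / √(2/9), and the rejection rates are about 8%, 17% and 51%.

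For r from 0.40 to 0.72 the sequence power stays at about 6%, 8–9% and 19–22%. It reaches 80% only for λ of about 2.4 to 2.6 SD.

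**The case against.** The strongest reply is that the practice row is not the root of the matter. The scanner task has 10 active blocks of 21 letters, or 210 trials, and the gabapentin-first group completes its first such run on gabapentin wherever the practice sits. The rule is simple, and the practice length is not stated, so its separate contribution is unknown. This stands: moving the practice is a partial remedy, and the error rates above cannot be assigned to the practice session.

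A reader might infer that the schedule by itself creates a biasing carryover. The documents do not support that. They call gabapentin well tolerated, contrast it with two drugs linked to cognitive dysfunction, and give no evidence that it alters learning of this task.

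A reader might also infer that having no practice at Visit 5 is a bias. It is not: a difference common to both orders is a period effect, and it is modelled. A constant shift adds no noise to the association between GABA change and activation once period is in the model. Only person-to-person variation in practice gain would, and nothing in the documents allows that to be sized.

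The plan does include a sequence term and an examination of order effects. These can flag an order-specific shift but cannot correct it, and at this sample size they will usually miss one.

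Finally, Table 1 may not record every task exposure. It has no row for the mock-scanner session described under Potential Risks. That session is described as a check on claustrophobia and comfort, and no off-drug go/no-go training is mentioned anywhere.

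**Conclusion.** The point holds as a conditional weakness that is cheap to remove. Go/no-go training takes place on gabapentin or on placebo according to order. Any net order-specific shift λ at the second scan biases the direct gabapentin effect on the no-go versus go contrast by λ/2. Washout does not act on it, the period term does not absorb it, and the sequence term has about 6% to 20% power for shifts of 0.25 to 1.0 SD.

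These figures assume 1:1 order, 9 completers per order, a two-sided 5% level and the GABA planning correlation applied to a single activation summary. The shifts themselves are assumed values, and if λ is zero there is no bias. The reach is the go/no-go part of Hypothesis 2. GABA levels under Hypothesis 1 and the cannabis-cue task do not depend on this practice.

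**What to change.** In Table 1, move the go/no-go practice mark from Visit 3 to Visit 2, with a note that it precedes the first observed dose, or to Visit 1 beside STOP-IT and delay discounting. Everyone is then trained off study drug. Before the two scans, use the same brief refresher at Visits 3 and 5, or none at either.

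State the order allocation ratio. In C.2.f, add a sentence saying that the sequence term cannot rule out order-specific learning at this sample size. If the present schedule is kept, give the reason and show a first-scan-only comparison of the go/no-go contrast as a sensitivity analysis.

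The cost is one table row and a few minutes of visit time. The sample size and primary models do not change. What remains is any learning from the first in-scanner run, which rescheduling the practice cannot remove.

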## C.2.f. Statistical Considerations

**Sample Size Determination.** Data from an ongoing investigation of gabapentin for AUD (n=21), where participants are scanned prior to, and 2 weeks following, initiation of gabapentin treatment or placebo, were used to inform power calculations for the proposed study; as the study remains blinded, estimates of variability and correlation between scan 1 and 2 GABA concentrations were taken from the combined sample. An estimate of anticipated dropout was derived from [name] trial of lamotrigine in AUD+BD, where 20% of participants dropped out by week 3. According to these estimates, with 18 completers (23 enrolled with 20% dropout), the proposed study would have >80% power to detect a  $\geq 25\%$  increase in GABA given a  $\geq 0.60$  correlation of GABA estimates across scans (observed  $r = 0.72$ ). Gabapentin studies have found 25-50% increases in GABA.

**H-MRS/fMRI Processing.** MEGA-PRESS (GABA) data will be analyzed using the Gannet MATLAB toolbox and PRESS (GLU) data using LCModel 6.3. Metabolites with fitting uncertainties <20% will be retained. Within-voxel tissue fractions of gray and white matter and CSF will be calculated based on automated segmentation in Statistical Parametric Mapping 12 (SPM12, Wellcome Department of Cognitive Neurology). Metabolite concentrations will be normalized to the unsuppressed water signal and corrected for within-voxel CSF fraction. fMRI analysis will be completed in SPM12. Standard fMRI preprocessing including realignment, normalization, and smoothing will be performed. Preprocessed data will be analyzed within a general linear model mixed effects framework. For the CCR task, the main contrast of interest will be the cannabis vs. neutral images contrast. For the go no-go task, the main contrast of interest will be the no-go vs. go trial contrast. Following 1st-level analysis, subject-specific spatially-normalized contrast maps will be entered into 2nd-level, random-effects analyses. Condition parameter maps will be thresholded at  $p < 0.05$ , corrected for multiple comparisons.

**Data Analysis.** Generalized linear mixed effects models will be employed to assess the effect of gabapentin on dACC and rBG GABA levels (Hypothesis 1). As detailed above, whole-brain random-effects analyses will be conducted to assess the direct effect of gabapentin, as well as the direct effect of gabapentin-induced changes in GABA, on brain activation to cannabis and response inhibition (impulsivity) cues (Hypothesis 2). These analyses will be supplemented with a region of interest approach (extracting % signal change from participants’ H-MRS voxels) using the MarsBaR SPM toolbox. Primary models for Hypotheses 1 and 2 will contain the main effect of treatment, period (scan 1 v. scan 2), and sequence (gabapentin 1st v. placebo 1st) to ensure the crossover design and washout were successful. All models will be re-estimated with GLU levels entered in place of GABA (Exploratory Hypothesis 1). To synthesize hypotheses 1-2, mediation models will be estimated in which metabolite levels are posited as mediators of the association between medication treatment and brain activity to

cannabis and response inhibition cues. We will employ previously successful methods to minimize attrition, but mixed effects models can be used to provide valid estimates assuming data are missing at random^112.

Exploratory/covariate analyses. 1) Mood and substance use: It is likely that mood and substance use will vary within individuals, across visits. We will examine associations between mood (YMRS, MADRS), substance use (TLFB, UDS, EtG, Saliva), and GABA and GLU levels, and will evaluate mood and substance use variables as covariates in all analyses. Potential medication-related changes in anxiety (BAI), sleep (PSQI), and impulsivity will also be explored (Exploratory Hypothesis 2). 2) Age, sex, smoking status, AUD, anxiety disorder, concomitant medications. Age, sex, and smoking status have been associated with GABA and GLU levels in the extant literature. Co-occurring anxiety disorders and AUD are very common in individuals with BD and have been associated with GABA/GLU dysregulation. Participants with anxiety and AUD will not be excluded to enhance feasibility/clinical generalization. Given the within-subjects design of the study, between-subjects variables are not potential confounders; nonetheless, we will consider these variables as moderators in all analyses. Potential indications of sex differences will be considered in future, larger studies.

**C.2.g. Potential Limitations.** 1) Previous studies that have demonstrated gabapentin-induced increases in brain GABA have been conducted in controls and epileptics. Whether these findings will generalize to CUD+BD is unknown. 2) Mood and substance use are potential confounders of condition comparisons as they can change over the course of the study in a given individual. Their impact on study outcomes will be carefully examined and they will be evaluated as potential covariates in all models. 3) A potential challenge to completing the study will be recruiting/retaining a sufficient number of CUD+BD participants. If recruitment goals are consistently not met, the study team will meet to discuss strategies for meeting goals without compromising the integrity of the study.

**C.2.h. Future Directions.** Positive results may support investigation of gabapentin for the treatment of CUD+BD in large RCTs. The proposed study may also provide successful demonstration of a multimodal imaging platform for evaluating the promise of other GABA/GLU drugs for CUD and/or BD. This study will also add to the literature on associations between GABA/GLU and RDoC constructs central to CUD/BD (impulsivity and cue reactivity).

**C.2.i. Timeline.** Purchasing, setup, and regulatory approval will be completed within the first 3 months of Yr 01. 11-12 participants will be recruited/year. Analysis and manuscript submission will begin in the 2nd half of Yr 02.

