**A.2. GABA and GLU Dysregulation in CUD and BD.** GABA and GLU, the main inhibitory and excitatory neurotransmitters (NTs) in mammals, respectively, are principally involved in the coordination of cortical activity, synaptic plasticity and modulation of other NT systems. The extant literature supports a role for dysregulated GABA and GLU transmission in CUD and BD. Preclinical research suggests that the reorganization of reward circuitry in substance use disorders (SUD) to preferentially respond to drug cues, manifesting clinically as drug craving and seeking, may be due to substance-induced neuroplasticity mediated by GLU and GABA. Cannabinoids have been shown to decrease GABAA-mediated inhibitory, and NMDA/AMPA-mediated excitatory, transmission via activation of cannabinoid type-1 (CB1) receptors located on presynaptic GABA/GLU neurons that are particularly abundant in cortex and basal ganglia (BG). BD studies have demonstrated links between genes responsible for coding ionotropic GLU receptor subunits, BD, and lithium response, as well as reduced levels of cerebrospinal fluid (CSF) and plasma GABA and differences in GABA receptor genes. Proton Magnetic Resonance Spectroscopy (H-MRS) studies provide the opportunity to better understand these issues in humans. H-MRS studies in CUD individuals have demonstrated decreased GLU and GABA levels in anterior cingulate cortex (ACC) as well as decreased GLU in right BG (rBG). H-MRS studies of BD have demonstrated elevated prefrontal GLU across mood states, and state-of-the-art (MEGA-PRESS) GABA studies have found abnormal ACC and occipital cortex GABA levels as well. Impulsivity, the tendency to respond without forethought, has been hypothesized as a “critical link” between SUD and BD; it is a core neurobehavioral feature of both CUD and BD and is causally related to GABA/GLU function. Preclinical studies have shown that injections of NMDA receptor antagonists, as well as the GABAA receptor agonist muscimol, are associated with impulsive behavior. H-MRS studies have demonstrated a positive association between anterior cingulate cortex (ACC) glutamate and impulsivity and a negative association between dorsolateral PFC and ACC GABA and impulsivity across clinical populations. Finally, fMRI investigations, which have primarily focused on the response inhibition facet of impulsivity, have consistently demonstrated differences in prefrontal activation to inhibition cues in both BD and CUD individuals relative to controls. In sum, studies have found that CUD and BD are each associated with prefrontal GABA/GLU disturbances and that impulsivity, a core neurobehavioral feature of both CUD and BD, is causally related to GABA/GLU function. Medications that normalize brain GABA/GLU may, therefore, impact clinical outcomes in CUD and BD both directly and indirectly through their impact on impulsivity (a key Research Domain Criteria [RDoC] construct).

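### The mediation models name metabolite levels as mediators in a two-scan crossover without separating within-person from between-person association; taken literally, the metabolite-to-BOLD path is not protected by randomised order

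*Combined protocol and SAP*

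**What the plan says.** The mediation plan is a single sentence in C.2.f, Data Analysis. To tie Hypotheses 1 and 2 together, "mediation models will be estimated in which metabolite levels are posited as mediators" between medication and activation to cannabis and response-inhibition cues. It does not say whether the mediator is the value at each scan, a gabapentin-minus-placebo difference or a person-centred value.

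The Hypothesis 2 analysis in the same paragraph is worded differently. It tests "the direct effect of gabapentin-induced changes in GABA, on brain activation", which is a within-person quantity. For the exploratory glutamate work, "All models will be re-estimated with GLU levels entered in place of GABA".

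The exploratory/covariate paragraph of C.2.f states: "Given the within-subjects design of the study, between-subjects variables are not potential confounders". Those variables are to be considered as moderators. C.2.g uses the same idea for a narrower target: "Mood and substance use are potential confounders of condition comparisons".

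**The concern.** Randomising the order of conditions makes the gabapentin-placebo contrast a comparison within each person. That protects the treatment effect on the metabolite and the treatment effect on BOLD. It does not protect the association between metabolite and BOLD, because nobody is randomised to a GABA level. A person with habitually low GABA may also have habitually different activation, for reasons unrelated to the drug.

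If the metabolite enters as a raw level, one coefficient has to serve both associations. A stable trait correlation could then be read as evidence that changing GABA changes brain activity. The statement that "Given the within-subjects design of the study, between-subjects variables are not potential confounders" is right for the treatment contrast but does not extend to this path. Planned covariates and moderators do not separate the two associations, and they cannot remove unmeasured trait differences.

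The documents give some reason not to assume that the trait part is zero. A.2 reports a negative association between frontal "GABA and impulsivity across clinical populations", and the go no-go task is the plan's probe of impulsivity. C.2.f adds: "Age, sex, and smoking status have been associated with GABA and GLU levels in the extant literature". Neither statement is a GABA-BOLD correlation.

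**Working it through.** **Inputs from the plan (C.2.f, Sample Size Determination).** 23 enrolled, 20% dropout, 18 completers; more than 80% power for a 25% rise in GABA; between-scan GABA correlation r of at least 0.60 assumed, 0.72 observed in a blinded pooled AUD sample.

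**The plan's own figures.** 18 / 0.8 = 22.5, rounded up to 23, so enrolment reproduces. The power claim cannot be checked directly because no SD is given. At two-sided 0.05 it holds if the coefficient of variation of GABA is at most about 0.40 (r = 0.60) or 0.48 (r = 0.72). No power figure is given for the mediation.

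**Why levels mix the two associations.** With two scans per person and a random intercept, the coefficient on raw GABA is approximately

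w × (between-person slope) + (1 − w) × (within-person slope),

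where w = λ(1 + r) / [(1 − r) + λ(1 + r)], λ = (1 − ρ)/(1 + ρ), and ρ is the residual intraclass correlation of BOLD. With ρ assumed to be 0.5, λ = 1/3:

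- r = 0.60: 0.533 / (0.40 + 0.533) = 0.57
- r = 0.72: 0.573 / (0.28 + 0.573) = 0.67

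Over ρ from 0.7 down to 0.3, w runs from 0.41 to 0.77. Without a random intercept it is (1 + r)/2, which is 0.80 or 0.86. So about half or more of the estimate usually comes from differences between people.

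**Simulated false-positive rates.** 18 completers, 9 per sequence, no true within-person effect, 3000 trials per cell. GABA r is 0.60 or 0.72. The GABA shift is 0.63 SD, from the standardised paired difference that gives 80% power: 0.70 × √(2 × 0.40) = 0.63. The assumed inputs, which the documents do not give, are BOLD reliability of 0.2 to 0.6 and the trait GABA-BOLD correlation. The level model is a REML random-intercept fit of BOLD on treatment, period, sequence and GABA (16 df). The within-person test regresses the BOLD difference on the GABA difference with sequence (18 − 3 = 15 df).

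| Trait correlation (assumed) | Level-based path | Within-person test |
|---|---|---|
| 0 | 4-6% | 4-6% |
| 0.2 | 7-10% | 4-6% |
| 0.4 | 10-19% | 4-6% |
| 0.6 | 17-41% | 4-6% |

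A separate simulation at trait correlation 0.5 and BOLD intraclass correlation 0.5 gave 22-27% for the random-intercept level model and 5% for the within-person model. Its mean level-based slope was 0.21 (r = 0.60) or 0.25 (r = 0.72), when the true within-person slope was 0.

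**From path to mediation claim.** These rates are for the metabolite-to-BOLD path alone. A mediation claim would normally also need a significant treatment-to-metabolite path. At this GABA shift that path has about 80% power at r = 0.60 and 92% at r = 0.72. If the two tests were independent, the top rate of 41%, which occurs at r = 0.72, would become about 0.92 × 41% = 38%.

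**Power of the within-person path.** With 18 pairs: 22% at a within-person correlation of 0.3, 37% at 0.4, 56% at 0.5 and 80% at about 0.62. At 0.62 it falls to 74% with 16 pairs and 66% with 14. A formula that treats the GABA differences as fixed gives 24% at 0.3, 63% at 0.5 and 80% at about 0.58. The differences are random here, so the lower figures apply.

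**The case against.** The strongest reply is that *levels* is shorthand. The glutamate sentence, "All models will be re-estimated with GLU levels entered in place of GABA", also covers the Hypothesis 2 model, which is about change, so the plan uses the word loosely. The mediation is there to synthesise a change-based hypothesis. This stands as a plausible reading, and under it there is no inflation. A reader might infer that the plan commits to uncentred levels; it does not. But the change wording is not carried into the mediation sentence, and an analyst who followed that sentence exactly would enter levels.

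Second, the link from GABA to BOLD is already tested in Hypothesis 2 through "the direct effect of gabapentin-induced changes in GABA, on brain activation". This also stands. A reader might infer that every GABA-BOLD analysis is affected; the documents do not support that. A spurious level-based path would sit beside a change-based result.

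Third, the size rests on assumed inputs. The cited associations are of GABA with impulsivity and of age, sex and smoking with metabolites, not of GABA with BOLD. The 41% figure needs the top of the assumed ranges (trait correlation 0.6, BOLD reliability 0.6) together with r = 0.72, and it is not a rate of false mediation claims.

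Fourth, a reader might add the 23 − 18 = 5 expected non-completers as single-scan participants and quote higher rates. The plan does not say that dropouts complete scan 1. The first scan is at Visit 3, so some may have none. No such rates are used here.

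Finally, the within-person path is itself observational. If variation in drug exposure moves both GABA and BOLD and induces a correlation of 0.5 between the differences, the recommended test would reject about 56% of the time with no GABA effect. This stands as a limit on the fix.

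**Conclusion.** The point holds for the mediation models only, and only if levels are entered as written. In that case the metabolite-to-BOLD path mixes between-person and within-person association, and the crossover does not protect the between-person part. The inflation is nil at a trait correlation of 0, small at 0.2 and material from about 0.4. The trait correlation and BOLD reliability are assumptions, and both values of r are assumptions for this population. There is no bias if the within-person and between-person slopes are equal. The rate of false mediation claims is lower than the path rate because a second path must also be significant.

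The statement on between-subjects confounders should not be read as an error in general: it is correct for condition comparisons, the use made in C.2.g. Hypothesis 1, the Hypothesis 2 change analysis, the sample size and the stated power are untouched. The remedy is a better-defined path at the cost of a few lines, so it is worth making before the data are seen.

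**What to change.** In the mediation models, enter the person-mean metabolite and the within-person deviation as separate terms, and test the deviation. For completers this is equivalent to regressing the gabapentin-minus-placebo BOLD difference on the gabapentin-minus-placebo metabolite difference, with sequence in the model (15 df with 18 pairs). Apply the same coding to glutamate. Limit the sentence on between-subjects confounders to the treatment contrast.

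The cost is SAP wording and one variable derived from data already planned. Three downsides should be stated:

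- Participants with one usable scan, whether through dropout or the spectral fit-quality cut-off, do not inform this path. They can stay in the Hypothesis 1 mixed models, where "mixed effects models can be used to provide valid estimates assuming data are missing at random" still applies.
- Power is low, as shown above, so a null result on this path would say little.
- The path remains observational, because variation in drug exposure could move both GABA and BOLD.

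A rule requiring both paths to be significant, a checked interval for the indirect effect, an exploratory label and a power statement would be reasonable additions, but they are optional.
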